9 STATISTICAL CONSIDERATIONS

9.1 General Design Issues

This is a clinical trial (CT) to evaluate the feasibility and begin to evaluate the effect of early sensorimotor intervention (SMI) for infants with HIE.

Primary Endpoint:

- Assessment 3 when the infants are 6 months of age and infants have completed the intervention

Secondary Endpoints:

- Assessment 1 at NICCU discharge when infants have completed the NICCU intervention
- Assessment 2 when the infants are 3 months of age and have completed part of the intervention.

Refer to Study Objectives on page 3 for primary and secondary hypothesis.

Refer to Outcome Measures on pages 12-14 for alphabetical list of outcome measures with validity and reliability data.

9.2 Sample Size and Randomization

No power analysis is included as this is a pilot study.

Refer to Enrollment, Baseline, and/or Randomization on page 11 for details on enrollment.

The assessors will not discuss intervention with the interventionist. Some assessments will be videotaped and scored via video by coders.

9.3 Interim analyses and Stopping Rules

The study will be stopped if there is a high number of SAEs overall, the number of occurrences of a particular type of SAE, severe AEs/reactions, or increased frequency of events. Such findings will be presented to the study statistician to review the events by group to determine whether there are statistical as well as clinical concerns. The statistician will report his findings to the Safety Officer and/or funding agency. The findings will be used to determine what steps will be taken.

9.4 Outcomes

Refer to Outcome Measures on pages 12-14 for alphabetical list of outcome measures with validity and reliability data.

9.5 Data Analyses

Descriptive statistics will be used to describe the study sample. All outcome measures will be reviewed for outliers and assessed for normality.

Given the small sample size, means and standard deviations (SD), frequency and proportions will be compared without statistical analysis depending on assessments of normality. Bayley-4 motor and cognitive composites will be quantified at 6 months for use in future clinical trial planning.

Primary Objective: Feasibility Aims

1. Is it feasible to complete 1 baseline survey, 1 assessment and 2 parent/therapist collaborative SMI intervention sessions with infants with moderate or severe HIE prior to NICCU discharge?
H1: $\geq 80\%$ of eligible infants will enroll and complete 1 baseline survey, 1 assessment and 2 intervention visits. - This will be assessed using frequency and proportions.

2. What proportion of parents complete $\geq 80\%$ of the recommended SMI intervention?
H2a: Parent/infant dyads will complete at least 8 of 10 recommended visits with the therapist. - This will be assessed using frequency and proportions.
H2b: Parents will report daily completion of interventions on 80% of randomly sampled days. - This will be assessed using frequency and proportions.
3. What proportion of parents complete 100% of the baseline and 3 assessment visits?
H3a: Parent/infant dyads will complete the baseline and 3 assessment visits.

Secondary Objectives:

4. Is it feasible to evaluate the impact of brain lesion location on response to intervention?
H4: $\geq 50\%$ of enrolled infants will have an MRI with tractography and cortical volume measurement post therapeutic hypothermia. - This will be assessed using frequency and proportions.

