- To assess the feasibility of evaluating the impact of brain lesion location on response to intervention (Aim 4), data from the magnetic resonance imaging (MRI) scan that is provided to all infants with HIE post therapeutic hypothermia or NE at CHLA will be analyzed to characterize the degree of HIE brain injury or NE and involvement of specific motor regions of the brain.

Interventions and Duration

All infants will receive the therapeutic intervention that is typically provided (standard care) in the CHLA NICCU and community, and infants in this trial will receive an additional 2 SMI intervention sessions in the CHLA NICCU and 8 SMI intervention sessions in the home, at CHLA, or at the University of Southern California (USC) Health Sciences Campus over the first 6 months of life at 1, 3, 5, 8, 11, 15, 20, 26 weeks post NICCU discharge. They can also occur via telehealth. If the infant is referred by a local NICU, they will omit the 2 SMI intervention in at CHLA. These 10 1-hour sessions will be provided by a licensed physical or occupational therapist and will consist of supporting parents to provide their infants with daily opportunities for positive sensory experiences and therapeutic play to enhance development. If the infant is at CHLA at 2 weeks after therapeutic hypothermia, the sessions can be done at CHLA or via telehealth until the child is discharged home.

Sample Size and Population

Twenty infants with HIE or NE and their parents (dyad) will participate in this clinical trial.

STUDY TEAM ROSTER

Principal Investigator: [name], PT, FAPTA

[name]

[contact]

[contact]

Main responsibilities/Key roles: coordinating and ensuring progress of the entire study with a focus on the intervention team

Co-Investigator/ MPI on grant: [name], PT – listed on ceded USC IRB

[name]

[contact]

[contact]

Main responsibilities/Key roles: coordinating and ensuring progress of the entire study with a focus on the assessment team

Co-Investigator: [name], OTR/L, CNT

[name]

[contact]

Main responsibilities/Key roles: coordinating the two intervention sessions in the CHLA NICCU; collecting parent-report outcome measures during the NICCU stay

Co-Investigator: [name], PT, DPT, PhD

[name]

[contact]

Main responsibilities/Key roles: analyzing parent report data

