1 STUDY OBJECTIVES

1.1 Primary Objective

Primary Objective: Feasibility Aims

1. Is it feasible to complete 1 baseline survey, 1 assessment and 2 parent/therapist collaborative SMI intervention sessions with infants with moderate or severe HIE or NE prior to NICCU discharge?
H1: $\geq 80\%$ of eligible infants will enroll and complete 1 baseline survey, 1 assessment and 2 intervention visits.
2. What proportion of parents complete $\geq 80\%$ of the recommended SMI intervention?
H2a: Parent/infant dyads will complete at least 8 of 10 recommended visits with the therapist.
H2b: Parents will report daily completion of interventions on 80% of randomly sampled days.
3. What proportion of parents complete 100% of the baseline and 3 assessment visits?
H3a: Parent/infant dyads will complete the baseline and 3 assessment visits.

Secondary Objectives

4. Is it feasible to evaluate the impact of brain lesion location on response to intervention?
H4: $\geq 50\%$ of enrolled infants will have an MRI with tractography and cortical volume measurement post therapeutic hypothermia.

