4.3 Study Enrollment Procedures

- The medical records of all infants with HIE or NE at the CHLA NICCU will be screened for eligibility, i.e. searching for infants who had a diagnostic/ICD-10 code associated with HIE, including neonatal encephalopathy, birth depression, intrapartum asphyxia.
- Parents of eligible infants will be taken to a private space, provided information about the study, and asked to consent to the study. Documentation of reasons for ineligibility and for non-participation of eligible candidates will be completed using a screening log in REDCap.
- Once consented, infants will receive standard care plus sensorimotor intervention (SMI). If referred by other local NICU, infants will follow the same procedure of consenting within 72 hours of discharge.

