6.2.2 Enrollment, Baseline, and/or Randomization

Enrollment

Enrollment is defined as the date that the parent/legal guardian agrees to participate and signs the consent form.

- Once consented, infants will be assigned to standard care plus sensorimotor intervention (SMI). If referred by other local NICU, infants will follow the same procedure of consenting and randomization within 72 hours of discharge.

General Assessment Information

All infants enrolled in the study will participate in the same assessment schedule. An assessor blinded to previous assessments will conduct all assessments. Inter-rater reliability on 10% of the visit will be assessed through scoring of videotaped

assessments. Given the high risk of cerebral palsy in this population, outcome measures described as “Highly Recommended” by the NINDS Common Data Elements for Cerebral Palsy were used for each domain.

The assessors will not discuss intervention with the interventionist. Some assessments will be videotaped and scored via video by coders.

For standardized assessments completed in the CHLA NICCU (Test of Infant Motor Performance, General Movement Assessment), they will be completed by a trained, licensed occupational or physical therapist with privileges in the CHLA NICCU and experience handling infants who are medically fragile.

If parents request information from the standardized assessments, the scores of the Test of Infant Motor Performance and Bayley Scales of Infant and Toddler Development can be provided. The PI will share the information with the participant via phone.

Description of All Assessments (alphabetical order)

Activity log. Parents will be asked to complete a log of their child’s activities across one day per week, randomly selected, for the 26 weeks from baseline to the end of intervention. Parents who have a smartphone will be offered a free, custom designed smartphone app and will be sent an alert to complete the log reflecting activity in the last 12 hours.²⁰ Parents without a smartphone or who prefer email will be sent an email to a REDCap survey to complete the log.

Affordances in the Home Environment for Motor Development Infant Scale (AHEMD-IS) Inventory: AHEMD is a standardized questionnaire used to quantify access to types of toys or environments in the home. Parents complete this questionnaire at NICCU discharge, and when the infant is 3 months and 6 months of age, via REDCap.

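### H1 holds uptake and completion together to one 80% threshold over eligible infants, so with observed consent below 80% it fails however well the NICCU components are delivered

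*Combined protocol and SAP*

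**What the plan says.** The Aim 1 question in section 1.1 concerns delivery: "Is it feasible to complete 1 baseline survey, 1 assessment and 2 parent/therapist collaborative SMI intervention sessions" before the infant leaves the NICCU. The matching hypothesis, stated in section 1.1 and repeated in section 9.5 with its analysis, sets a threshold of at least 80% "of eligible infants will enroll and complete 1 baseline survey, 1 assessment and 2 intervention visits. - This will be assessed using frequency and proportions".

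Other parts of the plan fix what the numerator and denominator mean:

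- Section 6.2.2: "Enrollment is defined as the date that the parent/legal guardian agrees to participate and signs the consent form". The enrolment part of H1 is therefore the consent rate.
- Section 4.3 has parents of eligible infants approached for consent, and states: "Documentation of reasons for ineligibility and for non-participation of eligible candidates will be completed using a screening log in REDCap". On this wording a family that declines is still eligible.
- Section 4.1 lists signed consent as the first inclusion criterion. On that wording a family that declines is not eligible.
- Précis, Sample Size and Population: "Twenty infants with HIE or NE and their parents (dyad) will participate in this clinical trial".
- Section 9.2: "No power analysis is included as this is a pilot study".
- The Précis (Interventions and Duration) and sections 3 and 5.1 say that infants referred from other local NICUs skip the two CHLA NICCU sessions.

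No completion threshold for the NICCU components is set among enrolled dyads. H4, by contrast, does use enrolled infants as its denominator.

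**The concern.** The question and its criterion measure different things. Whether two sessions, a survey and an assessment fit into a short stay depends on delivery. The H1 proportion also depends on how many families agree to join a study. One figure against one threshold cannot show which of the two fell short.

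No test or interval is planned, so the comparison of the observed proportion with 80% is the whole of the prespecified answer to the first primary aim. If consent is modest, that answer is negative even when every enrolled family completes everything. A completion criterion chosen afterwards to repair this would be post hoc. Referred infants add a second route to failure that also says nothing about delivery in the CHLA NICCU.

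**Working it through.** **Inputs.** From the documents: threshold 80% of eligible infants (1.1, 9.5); 20 enrolled dyads (Précis); enrolment equals consent (6.2.2); referred infants omit the NICCU sessions (Précis, 3, 5.1). Neither the 20 nor the 80% is derived, so there is no figure of the plan's own to reproduce. The consent rate is not documented; 60% to 90% is assumed.

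**Step 1: identity.** H1 proportion = completers / eligible = (enrolled / eligible) × (completers / enrolled) = consent × completion. Completion cannot exceed 1, so the H1 proportion cannot exceed observed consent. If observed consent is below 80%, H1 fails. Otherwise the completion needed is 0.80 / consent: 100% at consent 80%, 89% at 90%, and 80% at 100%.

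**Step 2: limits with 20 enrolled.** The largest eligible count that still meets H1 is completers / 0.80, rounded down.

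| Completers of 20 | Most eligible infants | Consent then needed |
|---|---|---|
| 20 | 25 | 80% |
| 19 | 23 | 87% |
| 18 | 22 | 91% |
| 17 | 21 | 95% |
| 16 | 20 | 100% |

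A sixth refusal gives 20/26 = 77% and fails H1 with perfect delivery. With 16 completers, one refusal gives 16/21 = 76%.

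**Step 3: chance of meeting H1.** Families are approached until 20 consent. The eligible count is 20 plus a negative binomial number of refusals, and completers are Binomial(20, completion). This assumes independent families, no referred infants and no replacement. The last column, 100% consent, is for reference.

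| True completion | Consent 60% | 70% | 80% | 90% | 100% |
|---|---|---|---|---|---|
| 100% | 0.03 | 0.19 | 0.62 | 0.97 | 1.00 |
| 90% | 0.006 | 0.05 | 0.21 | 0.59 | 0.96 |
| 80% | 0.001 | 0.01 | 0.06 | 0.24 | 0.63 |
| 50% | <0.001 | <0.001 | <0.001 | 0.001 | 0.006 |

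**Step 4: referred infants.** In H1 a referred infant counts as a non-completer. If nobody declines and every CHLA infant completes, four referred among 20 give 16/20 = 80%, which just passes. Five give 15/20 = 75%, which fails.

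**Step 5: the same 80% among enrolled dyads.** With 20 CHLA NICCU dyads the criterion is at least 16 of 20. It is met with probability 0.96, 0.63, 0.24 and 0.05 at true completion of 90%, 80%, 70% and 60%, whatever the consent rate. The exact 95% interval is 56% to 94% for 16/20 and 83% to 100% for 20/20. With fewer such dyads the count changes: with 16 dyads, 0.80 × 16 = 12.8, so at least 13.

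**The case against.** **The denominator may not include families who decline.** Section 4.1 makes consent a condition of eligibility, and on that reading H1 is already completion among the consented. Against this, H1's own requirement to enrol would then be empty, and section 4.3 speaks of eligible candidates who do not participate. The consent-times-completion reading is the better one, but the two sections differ and the plan should settle it.

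**Enrolment is part of feasibility.** This stands. With a short stay, failing to reach and consent a family in time is itself a limit on the NICCU phase. It is a reason to report uptake and the joint proportion, but not to let them stand in for completion.

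**The components are already collected.** This also stands. The screening log records non-participation, and the Précis promises reporting of session timing and participation. What is missing is a prespecified completion criterion for the NICCU components among enrolled dyads.

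**Exactly 20 enrolled is an assumption.** Section 8 allows some consented dyads who receive no intervention to be replaced, so the number enrolled may exceed 20. The counts in step 2 would then shift; the ceiling in step 1 would not.

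**Stronger readings to avoid.** A reader might infer that any usual consent rate sinks H1. The documents give no rate, and at 90% consent with full completion H1 is met with probability 0.97. A reader might infer that H1 never separates good delivery from poor. At 90% consent it does: 0.97 with full completion against 0.001 with half. A reader might infer that failing H1 would stop the programme. No go/no-go rule is tied to H1; it is a descriptive benchmark.

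**Conclusion.** The point holds in a limited form. H1 does not answer the question that Aim 1 asks. Whenever observed consent is below 80%, its result is negative regardless of delivery. Above 80%, the completion it requires varies from 100% down to 80% as consent rises, so meeting or missing it has no fixed meaning for delivery. The ceiling needs no assumed consent rate, only that families who decline count as eligible. The probabilities rest on the assumed 60% to 90% range and on the model in step 3. If referred infants are counted, five among 20 enrolled put H1 out of reach. The fault lies in the criterion, not in the data, and it should be corrected before the results are read.

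**What to change.** In sections 1.1 and 9.5:

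- Define eligible, for H1, as meeting the section 4.1 and 4.2 criteria other than consent, so that 4.1 and 4.3 agree.
- **H1a, uptake:** enrolled divided by eligible, from the screening log.
- **H1b, completion:** the proportion of enrolled CHLA NICCU dyads who complete the baseline survey, Assessment 1 and both NICCU sessions. Apply the 80% criterion for Aim 1 here, to the actual number of such dyads, with an exact 95% interval. Exclude referred infants and report them separately; otherwise H1b would inherit the automatic failure in step 4.
- Keep the joint proportion over eligible infants as a reported figure.

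The cost is small: rewording and one definition. Uptake and completion come from the screening log and the study's REDCap records; referral source must be identifiable for each dyad. The downsides are that more than one figure is reported, the H1b denominator may be below 20 and its interval correspondingly wide, and the Aim 1 verdict no longer covers recruitment, which H1a and the joint figure then report.

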4 SELECTION AND ENROLLMENT OF PARTICIPANTS

4.1 Inclusion Criteria

To be eligible to participate, an individual must meet all of the following criteria:

1. One adult parent/legal guardian has provided signed and dated informed consent form agreeing to the child's participation and the parent's own participation. If a parent/legal guardian is providing consent for a child's participation and a different adult caregiver will be participating, the other adult caregiver must consent to their own participation
 - a. A parent/legal guardian must be willing to also be enrolled in the study and be legally able to consent to their own participation in the research (18 years or over). Parents/legal guardians who are under 18 years and remain in the care of their parents are likely to have a different level of caregiving and support than those who are adults which may impact the delivery of the intervention and assessment visits. If one parent is over 18 years, that parent can participate.
 - b. Inclusion criteria for the adult is that they will be a caregiver for the enrolled infant
 - c. Stated willingness to comply with all study procedures and availability for the duration of the study
2. Infants with HIE based on the modified Sarnat Exam on admission¹⁷ and has started to receive therapeutic hypothermia for 72 hours.¹⁸ Or infants with neonatal encephalopathy.
3. Cared for in the Newborn and Infant Critical Care Unit (NICCU) at Children's Hospital Los Angeles (CHLA) or by referral from other local NICUs.
4. Family lives within 60 miles of CHLA.

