Medical Record Review / Medical Updates. A combination of medical records and parent interview will be used to describe the medical history of enrolled participants using the F2203_Medical History and F2207_Surgical and Hospitalization History. While infants are in the NICCU the medical record will be used exclusively (baseline and NICCU discharge assessments). After NICCU discharge parents will be asked to complete these forms via REDCap when the infant is 3 and 6 months of age. Parents will be asked for HIPAA authorization for the research team to attain the following medical records to describe the participants: NICCU discharge summary and neurology, neuroimaging and High-Risk Infant Clinic reports through 2 years of age.

Neuroimaging Data Collected as Part of Routine Clinical Care. Neonates will undergo magnetic resonance imaging (MRI) using a standardized MRI protocol, which was developed for use across sites and MRI platforms as part of the NIH-funded phase III High-dose Erythropoietin for Asphyxia and Encephalopathy (HEAL) Trial. This protocol includes: structural T1- and T2-weighted MRI scans, Diffusion Tensor Imaging (DTI) and MR Spectroscopy. Data from the participants will be processed offline by a single investigator ([name]) who is masked to the infant's history and clinical course. The locus and degree of brain injury will be scored using the Washington University HEAL scoring system. Additionally, regions of interest (ROIs) will be placed in the ventrolateral thalami, posterior putamen and corticospinal tract at the level of the midbrain (cerebral peduncles), posterior limb of the internal capsule and corona radiata and used to extract fractional anisotropy (FA), axial (AD) and radial diffusivity (RD). Together these data will be used to

characterize the degree of HIE brain injury and involvement of the corticospinal tract and deep gray nuclei (thalami, putamen). These variables will be tested as potential moderators of treatment effects in future studies.

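### H4 counts MRI measurements that the described image processing does not include, and its cooling condition leaves uncooled NE infants in the denominator with no way to qualify

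*Combined protocol and SAP*

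**What the plan says.** Aim 4 asks: "Is it feasible to evaluate the impact of brain lesion location on response to intervention". Its one hypothesis, H4, is worded the same way in the objectives (Section 1) and in 9.5. At least 50% "of enrolled infants will have an MRI with tractography and cortical volume measurement post therapeutic hypothermia".

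The imaging plan is in 6.2.2, under the routine-care neuroimaging entry. On acquisition it says: "This protocol includes: structural T1- and T2-weighted MRI scans, Diffusion Tensor Imaging (DTI) and MR Spectroscopy". On processing it says: "The locus and degree of brain injury will be scored using the Washington University HEAL scoring system". It adds that "regions of interest (ROIs) will be placed in the ventrolateral thalami, posterior putamen and corticospinal tract at the level of the midbrain" and at further corticospinal levels, from which FA, AD and RD are extracted. The same entry says that these variables are to be examined as moderators in later studies.

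On population, the précis states: "Twenty infants with HIE or NE and their parents (dyad) will participate in this clinical trial". Section 4.1 ties the HIE route to hypothermia having been started, then adds: "Or infants with neonatal encephalopathy". No cooling condition is attached to that second route. Section 4.1 also admits infants referred from other local NICUs. The précis describes the MRI as the "scan that is provided to all infants with HIE post therapeutic hypothermia or NE at CHLA".

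**The concern.** A feasibility criterion should count the thing whose feasibility is in question. Here that is whether lesion-location variables can be obtained often enough to support a later moderator analysis. H4 counts two other measurements. The lesion variables that the plan does extract do not enter it.

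The wording also brings in a treatment condition that eligibility does not require. An NE infant who was not cooled can be enrolled, scanned and scored for lesion location, and still be recorded as a failure.

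What is at stake is the reported answer to Aim 4. If someone decides after the scans are read what H4 was meant to count, the same data could be reported as meeting or missing the 50% mark, and the verdict would be post hoc.

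**Working it through.** **Inputs.** Planned enrolment is 20 (précis). The threshold is 50% (H4). The outputs come from 6.2.2 and eligibility from 4.1. The number of uncooled NE infants, *k*, is not given, so it is varied below as an assumption. The plan derives no power or precision figure that could be reproduced (9.2).

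**Step 1: threshold as a count.** 0.50 × 20 = 10 infants.

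**Step 2: H4 against the rest of the plan.**

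| H4 requires | Counterpart elsewhere in the plan |
|---|---|
| Tractography | DTI is acquired. The described step is FA/AD/RD from placed regions, some of them in the corticospinal tract. That is tract sampling at most; no tractography step is named. |
| Cortical volume | T1 and T2 images are acquired. No volumetric step is named. |
| Timing after hypothermia | Hypothermia is part of the HIE route only; the NE route has no cooling condition. |

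The first two requirements are joined by *and*, so the missing cortical volume is enough to stop an infant counting. In the text available, neither measurement is mentioned outside H4. Conversely, the HEAL score and the FA/AD/RD values are described in 6.2.2 and are absent from H4.

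**Step 3: effect of the cooling condition alone.** Suppose tractography and volumetry were done after all. With *k* uncooled infants in the denominator:

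- highest attainable proportion = (20 − *k*)/20
- rate needed among the others = 10/(20 − *k*)
- chance of reaching 10 = P(X ≥ 10), with X binomial (20 − *k*, *p*), where *p* is an assumed qualifying rate among the others

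| *k* | Highest attainable | Needed among others | Chance at *p* = 0.8 | Chance over *p* = 0.6 to 0.9 |
|---|---|---|---|---|
| 0 | 100% | 50% | 0.999 | 0.872 to 1.000 |
| 4 | 16/20 = 80% | 10/16 = 62.5% | 0.973 | 0.527 to 0.999 |
| 8 | 12/20 = 60% | 10/12 = 83.3% | 0.558 | 0.083 to 0.889 |
| 10 | 10/20 = 50% | 10/10 = 100% | 0.107 | 0.006 to 0.349 |
| 11 | 9/20 = 45% | 10/9, impossible | 0 | 0 |

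Each uncooled infant lowers the maximum by 1/20 = 5 percentage points. The criterion becomes unreachable for this reason alone at *k* = 11.

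**Step 4: after alignment.** If H4 counted the outputs in 6.2.2 without the cooling condition, the threshold would still be 10 of 20. All 20 infants could in principle qualify, and the maximum would no longer depend on *k*.

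**The case against.** **The inputs for both measurements are acquired.** DTI and T1/T2 images could support tractography and volumetry, and 6.2.2 does not say that its list of processing steps is complete. A reader might infer that H4 is bound to score 0 of 20. The documents do not support that as a forecast. Zero describes the processing as written, and an added step would change it. H4 could also be read as asking only for a scan adequate for those measures, which would give neither 0 nor 100%, because a routine scan is not always usable. What stands is that the plan does not say which reading applies.

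**The lesion data will be collected anyway.** A reader might infer that Aim 4 cannot be answered. That goes too far. The précis assigns Aim 4 to MRI analysis of injury degree and motor regions, and 6.2.2 specifies that work, so the data can be reported whatever H4 says. The benchmark is mismatched; the assessment is not missing.

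**The cooling phrase may only describe scan timing.** Sections 3 and 9.1 still speak of HIE alone, so it may be wording kept from an HIE-only population. That is plausible, but as written it still works as a counting condition.

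**Referred infants.** It is tempting to add referred infants without a scan to the uncooled ones and say that both lower the maximum unfairly. That is not right. An enrolled infant without a scan is a genuine feasibility failure and should count as one. Section 6.2.2 also describes an MRI protocol built for several sites and platforms, although it does not say where referred infants are scanned.

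**Conclusion.** The concern holds as a mismatch between a success criterion and the plan's own measurements. An infant with complete HEAL and region-of-interest data does not meet H4 as worded, because cortical volume is required and no step to measure it is described. An uncooled NE infant cannot meet it under a literal reading of the cooling phrase.

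The size of the second effect is unknown. It is 5 percentage points off the maximum per uncooled infant, and decisive alone only from 11 of 20. The documents give no uncooled share, so the table shows a range and not an expectation.

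The matter should be fixed, but it is not critical. H4 is a secondary, descriptive benchmark in a pilot without a power analysis; 9.5 plans no statistical comparison, and no progression decision is tied to H4. No error rate, sample size or primary aim is affected.

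**What to change.** Before any imaging data are reviewed, restate H4 identically in Section 1 and in 9.5, for example: *At least 50% of enrolled infants have a usable neonatal MRI from which the HEAL injury score and the FA, AD and RD measures of 6.2.2 can be obtained.* Define *usable* and say how a scan with some unreadable regions counts. Failing an infant for one unreadable region would be a new and stricter rule, to be adopted only deliberately.

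If tractography and cortical volume are truly intended, add those processing steps to 6.2.2 instead. The documents do not show which the sponsor meant, and either route reconciles the sections.

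Under either route:

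- drop hypothermia as a counting condition
- keep all enrolled infants in the denominator and count unscanned referred infants as failures
- report the proportion by CHLA/referred and by cooled/uncooled, with the reason for each failure (for example not scanned, different protocol, motion)

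The first route uses variables that the plan already extracts and leaves the threshold at 10 of 20. Its cost is a wording change in two places, plus recording scan usability and the reason for each failure. The second route also adds image processing work.
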